## 10.8 **Duration of Patient Participation**

All patients will be permitted to remain on study to receive the investigational combination treatment as long as it is well tolerated and both the Investigator and Sponsor agree that the patient may be clinically benefitting from treatment, for up to 2 years. Reasons for treatment discontinuation include, but are not limited to, the following:

- Unacceptable or Dose-Limiting Toxicity
- Disease Relapse or Progression
- Death
- Voluntary withdrawal of consent
- Non-compliance to study procedures and requirements
- Investigator decision

• Sponsor decision to terminate the study

Unless a patient withdraws consent or dies during the treatment period of the study, she will be followed for up to 1 year after study treatment discontinuation for survival data.

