#### 24.3 Sample Size and Power

**Part A Safety Evaluation:** For the traditional 6+3 design of Part A, the goal is to determine a treatment schedule for which the rate of DLTs is less than 33% in 6 or 9 patients. A minimum of 6 patients are planned for Part A, with a maximum of 18 DLT-evaluable patients for the Starting Treatment Schedule and Reduction Level 1. If  $\geq$ 3 in 6 or 9 patients at Reduction Level 1 have DLTs, then the investigational treatment regimen will be considered too toxic and enrollment into the study will be discontinued.

Part B: Part B follows a 1-sided Simon 2-Stage design; 15 patients, including all patients from Part A without a DLT, who receive the recommended Phase 2 regimen and who meet the criteria for the Efficacy Evaluable Population (see Section 24.4), with HPV 16 or 18 positive advanced cervical cancer will be included in the first stage analysis. If 3 or more objective responses (PR or better) are observed in the first stage, another 13 patients will be enrolled into the second stage, for a total of 28 patients in Part B. Study has passed the first stage of Simon-Two stage design. For a null hypothesis ORR24 of 0.15 and an alternative hypothesis ORR24 of 0.35, the sample size of 28 patients will provide a one-sided significance level of approximately 5% and a power of 80%. If Stages 1 and 2 are completed, a minimum of 8 patients must demonstrate a response (PR or better) to reject the null hypothesis.

Part C: Part C is to evaluate efficacy in larger patient population. In Keynote-158 study (pembrolizumab monotherapy in patients who have progressed with standard of care systemic therapy), ORR in total patients (i.e. regardless of PD-L1 status) and with CPS  $\geq$  1 were 12.2% and 14.6%, respectively.

Given this, null hypothesis for  $ORR_{24}$  was set at  $P_0 = 12.2\%$ . With an alternative hypothesis for  $ORR_{24}$  of  $P_a = 37\%$ , the sample size of 60 subjects was calculated considering two-sided significance level of 0.05, 97% power, and 25% dropout rate.

The confidence interval (CI) for ORR24 will be estimated using exact Clopper-Pearson method, and if the lower bound of the two-sided 95% CI for ORR24 exceeds 12.2%, it will be proven to satisfy the primary efficacy.

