#### 24.4 Analysis Populations

Safety Population. All patients who receive at least 1 dose of 1 agent in the investigational treatment regimen (i.e. either GX-188E or P) will be included in the analysis of safety, regardless of the duration of treatment.

DLT-evaluable. Unless doses are missed within the first two weeks of treatment (i.e., Week 1 Day -1 to Week 2 Day 7) due to DLT(s), a patient must receive all of the planned administrations of both agents (GX-188E and P) within the DLT-evaluation period to be considered evaluable for DLT. If a patient misses any treatment within the first two weeks of the study for reasons other than a DLT, the patient will be considered non-evaluable for DLT and replaced.

Efficacy Evaluable Population. All patients who discontinue the study treatment regimen early due to treatment-related toxicity will be considered evaluable for efficacy. Patients who discontinue study due to disease-related death, unequivocal tumor progression or with at least 1 post-baseline tumor assessment must have received at least 45 days of treatment to be considered evaluable for efficacy. Patients in Part B and C who do not meet the aforementioned requirements will be considered non-evaluable for response and may be replaced. Patients from Part A, who receive the recommended Phase 2 regimen and who meet the aforementioned criteria for the Efficacy Evaluable Population will be included in the analysis for Part B and C. The following table provides further, more specific details.

Table 7. Determination of Patients to be Included in Efficacy Evaluable.

Patient Cohort	Reason for Discontinuation	Number of Days on Protocol Treatment	Include in Efficacy Evaluable Population (Yes/No)?
Part A receiving RP2 regimen*	Protocol-Defined Dose Limiting Toxicity (DLT), or other toxicity	Not applicable	Yes, included in Efficacy Evaluable Population
Part A receiving RP2 regimen*	Disease-related death, unequivocal tumor progression or at least 1 post-baseline tumor assessment	< 45 days	No
Part A receiving RP2 regimen*	Disease-related death, unequivocal tumor progression or at least 1 post-baseline tumor assessment	≥ 45 days	Yes, included in Efficacy Evaluable Population
Part A, receiving dose > RP2 regimen*	Any	Not applicable	No
Part B and C	Disease-related death, unequivocal tumor progression, or at least 1 post-baseline tumor assessment	< 45 days	No, patient may be replaced

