## Special notes on response assessment

When nodal disease is included in the sum of target lesions and the nodes decrease to 'normal' size (< 10 mm), they may still have a measurement reported on scans. This measurement should be recorded even though the nodes are normal in order not to overstate progression should it be based on increase in size of the nodes. As noted earlier, this means that patients with CR may not have a total sum of 'zero' on the case report form (CRF).

Patients with a global deterioration of health status requiring discontinuation of treatment without objective evidence of disease progression at that time should be reported as 'symptomatic deterioration'. Every effort should be made to document objective progression even after discontinuation of treatment. Symptomatic deterioration is not a descriptor of an objective response: it is a reason for stopping study therapy. The objective response status of such patients is to be determined by evaluation of target and non-target disease.

Conditions that define 'early progression, early death, and non-evaluability are study specific and should be clearly described in each protocol (depending on treatment duration, treatment periodicity).

In some circumstances it may be difficult to distinguish residual disease from normal tissue. When the evaluation of complete response depends upon this determination, it is recommended that the residual lesion be investigated (fine needle aspirate/biopsy) before assigning a status of complete response. FDG-PET may be used to upgrade a response to a CR in a manner similar to a biopsy in cases where a residual radiographic abnormality is thought to represent fibrosis or scarring. The use of FDG-PET in this circumstance should be prospectively described in the protocol and supported by disease specific medical literature for the indication. However, it must be acknowledged that both approaches may lead to false positive CR due to limitations of FDG-PET and biopsy resolution/sensitivity.

For equivocal findings of progression (e.g., very small and uncertain new lesions; cystic changes or necrosis in existing lesions), treatment may continue until the next scheduled

assessment. If at the next scheduled assessment, progression is confirmed, the date of progression should be the earlier date when progression was suspected.

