#### 5.4. EFFICACY EVALUABLE POPULATION

All patients who complete the study will be included into the efficacy evaluable population. These patients will be identified by using the "Subject's status?" with answer "Completed trial" from end of study page of CRF.

All patients who discontinue the study treatment regimen early due to treatment-related toxicity will be considered evaluable for efficacy. These patients will be identified as those with DLT. Patients who discontinue study due to disease-related death, unequivocal tumor progression or with at least 1 post-baseline tumor assessment must have received at least 45 days on protocol treatment to be considered evaluable for efficacy. Patients who discontinue study due to disease-related death will be identified by using the "Primary reason for premature discontinuation from study" with answer "Death" from end of study page of CRF and the "Was death disease related" with answer "Yes" from death details page of CRF. Patients who discontinue study due to unequivocal tumor progression will be identified by using "Primary reason for premature discontinuation from study" with answer "Disease Relapse or Progression" from end of study page of CRF. Patients who discontinue study with at least 1 post-baseline tumor assessment will be identified as those with at least one RECIST/iRECIST Overall Response data on RECIST/iRECIST Overall Response page of CRF after screening visit. Patients in Part B and Part C who do not meet the aforementioned requirements will be considered non-evaluable for response and may be replaced. Patients from Part A, who receive the recommended Phase 2 regimen and who meet the aforementioned criteria for the Efficacy Evaluable Population will be included in the analysis for Part B and Part C. The following table provides further, more specific details.

Document: \\ieedc-vnac01\Biosdata\Genexine\GX-188E\GYA02599\Biostatistics\Documentation\SAP

Author: [name] Version Number: 1.1

Version Date: 05Sep2022

Template No: CS\_TP\_BS016 Revision 6 Reference: CS\_WI\_BS005

Analysis Plan Page 16 of 48

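### Treated patients with no post-baseline assessment who stop for a reason outside Table 7 leave the primary ORR24 denominator at any treatment duration, which can only raise the estimate

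*Protocol*

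**What the plan says.** Protocol 24.5 restricts the population efficacy endpoints, including ORR24, to the Efficacy Evaluable set. Protocol 24.4 and Table 7 give the routes in for Parts B and C:

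- stopping for treatment-related toxicity, with no minimum duration and no scan needed;
- disease-related death, unequivocal progression or at least one post-baseline assessment, each with 45 or more days of treatment.

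SAP 5.4 adds patients who complete the trial. It also reads toxicity as DLT only, which is narrower than the protocol. For the remainder the protocol says "Patients in Part B and C who do not meet the aforementioned requirements will be considered non-evaluable for response and may be replaced", and the SAP agrees: "Patients in Part B and Part C who do not meet the aforementioned requirements will be considered non-evaluable for response and may be replaced".

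The stopping reasons in Protocol 10.8 go beyond that list. They include "Voluntary withdrawal of consent", non-compliance and investigator decision. Appendix 5 also sets apart "Patients with a global deterioration of health status requiring discontinuation of treatment without objective evidence of disease progression", to be reported as symptomatic deterioration. None of these has a row in Table 7 or SAP Table 1.

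The first scheduled on-study scan is at about 9 weeks (Protocol 22.1.2). Imaging is also requested when treatment stops (16.12 and 22.1.3). SAP 15 repeats ORR24 in the safety population as a sensitivity analysis.

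**The concern.** A patient who leaves without a post-baseline assessment, for a reason not on the list, is outside the primary denominator however long she was treated. Removing the 45-day threshold would not bring her in, because her reason is still not listed. The gap is therefore separate from that threshold.

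Response under RECIST needs a post-baseline assessment, so every patient in this group is a non-responder. Her exclusion lowers the denominator and leaves the numerator unchanged. The estimate then describes a selected part of the treated patients, while the Part C question is whether the regimen beats 12.2% in those who receive it. In advanced cancer, leaving before the first scan is plausibly linked to decline, so the loss need not be unrelated to outcome. At stake are the size of the reported ORR24 and the error rate of the Part C success rule.

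**Working it through.** **Inputs from the documents (Protocol 24.3).** Null 12.2%, alternative 37%. Success is declared "if the lower bound of the two-sided 95% CI for ORR 24 exceeds 12.2"%, by the Clopper-Pearson method. On size: "the sample size of 60 subjects was calculated considering two-sided significance level of 0.05, 97% power, and 25% dropout rate".

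**Assumption.** d is the share of treated patients excluded for an unlisted reason with no assessment. The documents do not give it. The 25% is total planned dropout, so it bounds d from above. The range shown is 0 to 25%.

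**1. The plan's own figure.** With n = 45, the smallest count whose two-sided 95% lower bound exceeds 12.2% is 11 (lower bound 12.9%). P(X ≥ 11 | 45, 0.37) = 97.4%, and 45/(1 − 0.25) = 60. The plan's N = 60 and 97% power are reproduced, with 45 evaluable out of 60 enrolled. If 60 are evaluable, the smallest passing count is 14 (lower bound 13.4%). Both cases are shown because Protocol 24.8 and SAP 4.3 wait for 60 evaluable patients.

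**2. Inflation factor.** If the all-treated rate is p and all excluded patients are non-responders, the rate in the analysed set is p/(1 − d).

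**3. Chance of meeting the Part C rule when the all-treated rate is 12.2%.**

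| d | Rate in analysed set | 45 evaluable, ≥ 11 | 60 evaluable, ≥ 14 |
|---|---|---|---|
| 0% | 12.2% | 1.7% | 1.2% |
| 5% | 12.8% | 2.45% | 1.8% |
| 10% | 13.6% | 3.5% | 2.8% |
| 15% | 14.4% | 5.0% | 4.2% |
| 20% | 15.3% | 7.2% | 6.5% |
| 25% | 16.3% | 10.3% | 9.9% |

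The nominal upper tail is 2.5%. It is passed just above d = 5% with 45 evaluable and at about d = 10% with 60. If 60 are treated and the excluded are not replaced, d = 10% leaves 54, at least 13 responders are needed, and the chance is 2.6%.

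**4. Effect on the estimate.** If the analysed set shows 37%, the all-treated rate is 0.37(1 − d) and the overstatement is 0.37d. The assumed effect is 37 − 12.2 = 24.8 points.

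- d = 10%: 33.3%, overstated by 3.7 points (15% of the effect).
- d = 15%: 31.5%, overstated by about 5.6 points (22%).
- d = 25%: 27.8%, overstated by about 9.3 points (37%).

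**5. Whether the denominator can decide the result.** Take the upper limit, 60 treated and 45 evaluable. Then 11/45 = 24.4% passes (lower bound 12.9%). The same 11 responders over 60 give 18.3% (lower bound 9.5%), which fails.

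**The case against.** The strongest reply is that the affected group may be small.

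- **Discontinuation scan.** Protocol 16.12 calls for imaging at the end-of-study visit whatever the reason for stopping, unless confirmed progression is that reason, and 22.1.3 asks for it when treatment stops. A patient with 45 or more days of treatment and that scan is included. The gap concerns only patients for whom this scan is missing too.
- **Recording of decline.** SAP 5.4 identifies progression from a CRF answer that covers relapse or progression, with no check for a scan. Appendix 5 asks for every effort to document progression. Clinical decline recorded under that answer enters at 45 days or more.
- **Sensitivity analysis.** The safety-population ORR24 would make the bias visible.
- **Size.** Nothing in the documents says that d is large, and at d = 10% the error rate is only 2.6% to 3.5%.

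All of this stands as a limit on size. None of it supplies a route in for the remaining patients, and the sensitivity analysis does not decide the primary test.

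A reader might also infer three stronger things that the documents do not support. First, ORR24 is not simply a rate among scanned patients: toxicity stops, and disease-related death or progression at 45 days or more, enter unscanned, while scanned patients under 45 days without toxicity are left out. Second, replacement is permitted, not required, and the bias arises from exclusion alone. Third, it is not established that a patient who stops for decline and dies later unscanned is excluded. SAP 5.4 uses the reason for leaving the study, Protocol 19.1 separates stopping treatment from leaving the study, and survival is followed for up to a year, so the end-of-study entry for such a patient is unclear.

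**Conclusion.** The gap is in the text of both documents, and its direction is certain: applied as written, the rule can only raise the primary ORR24. Its size is unknown because d is not given. With d up to about 5%, the chance of a false Part C success stays within the nominal 2.5%. At 10% it is modestly above, at 2.6% to 3.5% depending on the evaluable number. At 15% it is 4.2% with 60 evaluable or 5.0% with 45, and only at the 25% bound does it reach about 10%. A reader might take that last figure as the trial's error rate. The documents do not support this, since the 25% covers dropout of every kind. The calculation assumes that the excluded patients are all non-responders, which follows from their having no assessment, and that the true all-treated rate is exactly 12.2%. The change is worth making because the plan already produces the analysis it needs.

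**What to change.** For the Part C test against 12.2%:

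1. Make the primary denominator all treated patients on the recommended Phase 2 regimen, building on the safety-population ORR24 already planned in SAP 15.
2. Count every patient without a confirmed response within 24 weeks, including those with no evaluable post-baseline assessment, as a non-responder. Keep the SAP 15.1 rule that a first response within 24 weeks may be confirmed later.
3. Do not replace treated patients.
4. Keep the Efficacy Evaluable set as the sensitivity analysis.

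A new table row for unlisted reasons would not be enough. The rows of Table 7 and SAP Table 1 that exclude patients under 45 days must no longer govern the primary denominator. Otherwise an early consent withdrawal would count as a failure while an early disease-related death stayed out. The same applies to the statements in Protocol 22.2 and the synopsis, and in SAP 3.1 and 15.1, that remove patients whose response could not be confirmed.

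The cost is a protocol and SAP amendment, made after Part B Stage 1 has passed in an open-label trial, and a somewhat lower estimate. No new data are needed. With 60 treated, at least 14 responders required and 37% among the patients analysed now, power is P(X ≥ 14 | 60, 0.37(1 − d)): 96.5% at d = 10%, 93.6% at 15% and 81.7% at 25%. Here d covers all patients newly counted, taken as non-responders.

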# 24.5 Efficacy Analysis

Response to treatment will be evaluated using both RECIST v1.1 (Appendix 5) and iRECIST (Appendix 6). For each patient with objectively measurable disease and who meet the criteria for inclusion in the Efficacy Evaluable population (Section 24.44), response to therapy (overall

response within 24 weeks and best overall response), time-to-best-response, duration of response (DOR), progression-free survival (PFS), and overall survival (OS) will be calculated. Responses for patients who do not meet the criteria for inclusion into the Efficacy Evaluable population may also be described.

Definitions for response and survival outcomes are provided below:

### **Efficacy Endpoints for Individual Patients**

Endpoint	Definition
Overall Response within 24	The best objective response achieved within the first 24
weeks (OR 24 )	weeks of treatment initiation
Best Overall Response (BOR)	The best objective response achieved prior to study
	discontinuation
Time-to-Best Response (TTR)	Time from treatment initiation to the best objective
	response achieved. This endpoint is only determined for
	patients who have a PR or CR.
Duration of Response (DOR)	Time from documentation of objective tumor response
	(PR or CR) to disease progression. This endpoint is only
	determined for patients who have a PR or CR.
Progression-Free Survival (PFS)	Time from treatment initiation until documented disease
	progression or death
Overall Survival (OS)	Time from treatment initiation until death from any cause

The Kaplan-Meier method will be used to estimate the median Duration of Response (DOR), median Progression-Free Survival (PFS), and median Overall Survival (OS).

### **Endpoints for the Efficacy Evaluable Study Population**

Population efficacy endpoints will only include those patients who meet the criteria for inclusion in the Efficacy Evaluable population (Section 24.4). The definition of statistics calculated by the endpoints is as follows.

Statistics	Definition
Overall Response Rate within 24	The proportion of efficacy evaluable patients who
weeks (ORR 24 )	achieve an objective response (PR or CR) within the first
	24 weeks of treatment initiation
Best Overall Response Rate	The proportion of efficacy evaluable patients who
(BORR)	achieve an objective response (PR or CR) prior to study
	discontinuation
Median Progression-Free	Timepoint at which the probability of progression-free
Survival time (mPFS)	survival equlas to 50% in the efficacy evaluable
	population

6-month PFS rate	Probability that the progression has not occurred by 6 months	
Median Overall Survival time	Timepoint at which the probatility of survival equlas 50%	
(mOS)	in the efficacy evaluable population	
Disease Control Rate (DCR)	The proportion of efficacy evaluable patients who had a	
	CR, PR or Stable Disease	
Median Duration of Response	Timepoint at which the probability of disease progression	
(mDOR)	equals 50% after documented objective tumor response	
	(PR or CR). This endpoint only includes patients who	
	have achieved an objective response. Kaplan-Meier	
	method will be used to estimate mDOR.	
Median Time to Best Response	Timepoint from treatment initiation to the best objective	
(mTTR)	response achieved (i.e., PR or CR whichever occurs	
	earlier) in 50% of patients. Median TTR will be	
	calculated using descriptive statistics in the population	
	restricted to subjects with the best objective response	

In addition, relationships between antitumor activity and exploratory biomarkers of immune system changes may be explored.

### 24.6 Safety Analysis

Safety variables to be analyzed are AEs, laboratory test results (e.g., hematology, coagulation, serum chemistry, thyroid function tests, and urinalysis), and vital signs. Clinically significant changes from baseline will be summarized using descriptive statistics.

Adverse event severity will be graded according to the CTCAE v4.0 or the most recent version and terms recorded on the CRFs will be mapped to preferred terms using the most recent version of the Medical Dictionary for Drug Regulatory Activities (MedDRA®). All AEs will be summarized according to the system organ class and preferred term within the organ class. Adverse events will be tallied for overall frequency (number and percentage of patients), worst reported severity, and relationship to the investigational study drugs for each preferred term per patient. Serious adverse events will be similarly summarized. Listings of deaths, SAEs, and AEs leading to early termination of study treatment or premature withdrawal from study will also be provided.

#### 24.7 Interim Analysis

An interim analysis will be performed with safety and efficacy data in case of at least 22 patients in efficacy evaluable population, after obtaining week 10 tumor assessment results (either by investigator/BICR).

